5. TRIAL OBJECTIVES AND CLINICAL HYPOTHESIS

5.1. *Trial Objective*

The objective of this study is to investigate the microbial contamination rates on the back surface of hydrogel and silicone hydrogel contact lenses extracted from Smart Touch Technology blister packs versus conventional lens packaging, and the impact of EDTA in the packaging solution after short-term placement on the eye (45 minutes), in a randomized, contralateral, investigator-masked non-dispensing study comprising of two visits.

5.2. *Clinical Hypothesis*

The microbial contamination rates on the back surface of soft contact lenses extracted from Smart Touch Technology blister packs will be lower compared to the microbial contamination rates on the back surface of contact lenses extracted from conventional lens packaging.

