6. TRIAL DESIGN

This will be a prospective, single centre, randomized, contralateral, investigator-masked non-dispensing study. This study requires three visits of approx. 1 hour duration each.

At the first visit, if possible, the order in which the hydrogel and silicone hydrogel contact lenses are allocated to the study participants will be randomized. At the second visit, participants will be crossed over to the alternate lens type (hydrogel or silicone hydrogel).

At each visit, participants will be instructed to:

- Wash their hands prior to handling the contact lenses;
- Swab their thumb and two index fingers of the hand routinely used to conduct contact lens insertion using a sterile cotton swab moistened with sterile preservative free saline for the evaluation of skin microbiota;
- Follow the manufacturer's guidelines for lens insertion;
- Open the blister pack and insert the contact lens randomly assigned for the right eye;
- Open the blister pack and insert the contact lens assigned for the left eye;
- Contact lenses will be removed aseptically by a masked investigator wearing sterile latex gloves, who is experienced in this technique, after 45 minutes of lens wear. All contact between the contact lens with the eyelids and eyelashes during lens removal will be avoided.

Lenses and finger swabs will be analysed for microbial contamination using established routine microbiology protocols. The number and species of organisms will be determined.

A minimum washout period of 48 hours will occur between the two study visits.

All proposed procedures conform to the NHMRC Statement on Human Experimentation.

Participants are considered enrolled when they have signed the informed consent form and are regarded as part of the clinical trial population.

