6.1. Methodology / Study Visits

6.1.1. Data Requirements per Visit

This study requires three visits of approx. 1 hour duration each. The data requirements for this visit are shown in Table 5.

Table 5

Procedure	Visit 1	Visit 2	Visit 3
Informed Consent	X		X
Demographics, ocular and medical history	X		
Update ocular and medical history		X	X
Spectacle vision	X	X	X
Slit lamp examination including fluorescein assessment	X	X	X
Randomization to contact lens material type*	X		
Randomization – assign eye in which to insert contact lenses retrieved from the two types of lens packaging	X	X	
Randomization – assign eye in which to insert each contact lens material extracted from the Smart Touch Technology blister packs			X
Study participant to wash hands and undergo finger swab	X	X	X
Study participant to insert contact lenses (including practice removing the contact lenses from the lens packages)	X	X	X
Vision with spectacles worn over contact lenses	X	X	X
Aseptic contact lens removal	X	X	X
Adverse event	*	*	*

* If applicable

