6.1.2. Randomisation and Masking

Prior to initiation of study treatment, each subject who provides informed consent will be assigned to a subject number that will serve as the subject identification number on all study documents. Subject numbers will be assigned in ascending order and should not be omitted or reused.

Participants will be randomly assigned to the lens packaging type to be inserted on each eye. A randomization scheme will be prepared in advance. In addition, if possible (dependent upon lens availability), participants will also be randomized as to the order in which the hydrogel and silicone hydrogel contact lenses are allocated at the first and second study visits.

Participants will practice the lens handling technique to remove a contact lens from the Smart Touch Technology blister pack. Once the participant is proficient with this technique, they will be instructed to follow the manufacturer's guidelines for insertion of the Smart Touch Technology contact lens, and to open the blister pack of the contact lens in the conventional lens packaging, scoop the lens out of the blister pack by placing a finger on the lens and sliding the lens up the side of the lens package until it is free of the container, and insert the contact lens on their eye.

The Investigator will provide instructions to the study participants as to the lens insertion technique but will not be cognizant to the randomisation schedule and will not be present during the lens insertion procedure to maintain masking.

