13.1.3. Analysis

Participants who complete the study treatment will be included in the analysis dataset. Reasons and frequency distribution of participants discontinued will be reported.

Overall contamination rates, expressed as a binary variable, and contamination rates for type of organism will be compared between the worn contact lenses extracted from the two different types of lens packaging, as

well as between the hydrogel and silicone hydrogel lens materials extracted from the two different types of lens packaging.

Data will be summarised as means \pm standard deviations for variables measured on an interval scale and median \pm inter-quartile range for ordinal variables. Statistical tests will be employed to determine significant differences between the worn contact lenses extracted from the two different types of packaging. Commonly used tests of significance at each visit may include paired t-tests and group t-test for parametric data and Wilcoxon sign rank test and rank sum test for non-parametric data.

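### Section 13.1.3 names only permissive per-visit tests, paired and unpaired, and no analysis that joins each participant's two packaging pairs to decide the single section 5.2 hypothesis

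*Combined protocol and SAP*

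**What the plan says.** **Design.** Section 6.1.2: "Participants will be randomly assigned to the lens packaging type to be inserted on each eye". In Table 5 (section 6.1.1), the row that reads "assign eye in which to insert contact lenses retrieved from the two types of lens packaging" is marked for visits 1 and 2 only. Section 6 moves participants to the other material at visit 2. Visit 3 is different: there the randomisation is to "assign eye in which to insert each contact lens material extracted from the Smart Touch Technology blister packs", so both eyes receive Smart Touch lenses and there is no packaging contrast.

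**Hypothesis.** Section 5.2 makes one statement about soft lenses as a whole, not split by visit or material: "The microbial contamination rates on the back surface of soft contact lenses extracted from Smart Touch Technology blister packs will be lower" than with conventional packaging.

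**Analysis.** Section 13.1.3 compares "Overall contamination rates, expressed as a binary variable", and rates by type of organism, between packaging types and between materials. On packaging it adds: "Statistical tests will be employed to determine significant differences between the worn contact lenses extracted from the two different types of packaging". The only tests named follow directly: "Commonly used tests of significance at each visit may include paired t-tests and group t-test for parametric data and Wilcoxon sign rank test", with the rank sum test completing the list. Section 13.1.2 sets significance at p of 5% or less and does not state sidedness. Section 13.1.3 analyses participants who complete the study treatment. Section 13.3 drops missing data points only from the analyses that need them.

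**The concern.** The 25 completers supply up to 25 x 2 = 50 packaging pairs, two from each person. The named tests are tied to each visit, and no model, stratified test or participant-level summary brings the two pairs together. If packaging is tested at visit 1 and again at visit 2, two p-values bear on one hypothesis. The plan does not say whether one visit, either visit, both visits or a pooled result decides.

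Two things are at stake. Each one-visit test uses half the pairs. And with the same true effect at both visits, the visits can disagree by chance, so the conclusion would depend on a rule chosen after the data are seen.

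A smaller point is that the group t-test and rank sum test sit in the same list, right after the sentence on packaging, and nothing keeps them away from this within-person comparison.

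**Working it through.** **The plan's own figure.** The 25 in section 13.1.1 cannot be reproduced. It is called an estimate, and no power, rates, between-eye correlation, sidedness or dropout is given. All rates and correlations below are therefore assumed, and tests are two-sided at 5%.

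**Step 1: hand check at 42% (conventional) v 23% (Smart Touch).** With between-eye correlation φ, one paired difference has variance

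p_C(1-p_C) + p_S(1-p_S) - 2φ√[p_C(1-p_C) p_S(1-p_S)].

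Here 0.42 x 0.58 = 0.2436, 0.23 x 0.77 = 0.1771, and √(0.2436 x 0.1771) = 0.2077. Power is about Φ(0.19/SE - 1.96), treating the two visits' differences as uncorrelated.

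| φ | Variance | SE, 25 pairs | Power | SE, 50 pairs | Power |
|---|---|---|---|---|---|
| 0.05 | 0.400 | 0.126 | 32% | 0.089 | 57% |
| 0.18 | 0.346 | 0.118 | 37% | 0.083 | 63% |
| 0.36 | 0.271 | 0.104 | 45% | 0.074 | 73% |

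The normal approximation is slightly optimistic for a t-test on 24 degrees of freedom.

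**Step 2: simulation.** 20,000 trials per setting, 25 participants, 2 visits, 2 eyes. Participant SD on the logit scale is 0, 1 or 2 (φ = 0.05, 0.18, 0.36 at 42% v 23%) and visit SD is 0.5. Marginal rates are held fixed, with the same packaging effect at both visits. The combined test is a one-sample t on each participant's mean difference; the one-visit test is a paired t. Triplets are SD 0/1/2. Repeat runs agree to within about 1.5 points.

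| Assumed rates | Combined power | One-visit power | Exactly one visit significant |
|---|---|---|---|
| 42% v 23% | 54/60/70% | 30/33/40% | 42/44/48% |
| 42% v 14% | 89/93/97% | 61/66/76% | 48/45/37% |
| 80% v 60% | 60/66/76% | 34/37/45% | 45/46/49% |
| 11% v 4.5% | 20/20/21% | about 11% | 19/19/18% |

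The last column follows from 2p(1-p): at p = 0.40, 2 x 0.40 x 0.60 = 48%. A different model (latent normal, 50% v 25%) gives the same pattern: 73-96% combined against 46-75% at one visit.

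**Step 3: how much the missing rule matters.** At 42% v 23%, counting a significant result at either visit gives 52/55/64% power; requiring both gives 9/10/16%. With no true effect and independent tests, an either-visit rule has a false-positive rate of 1 - 0.95² = 9.75% in either direction, and 1 - 0.975² = 4.9% in the hypothesised direction. Simulated two-sided rates are about 7-10% at common rates of 11-80% (about 4-5% in the hypothesised direction) and 2-3% at 4.5%. The combined test stays at 4.4-5.4% at 11-80%, and 2.2-4.1% at 4.5%.

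**Step 4: unpaired tests at one visit.** The unpaired SE ignores φ: √(0.4207/25) = 0.130, so power is about Φ(0.19/0.130 - 1.96) = 31% whatever the correlation. Simulated unpaired power is 31/30/28%, against 31/33/40% paired in the same run. At a common rate of 42%, unpaired type I error is 5.7/3.6/1.6%.

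**The case against.** **The list is permissive and may not be meant for the binary endpoint.** The sentence says what tests may include, and it speaks of parametric and non-parametric data after a line on interval and ordinal summaries. The sentences that set up the packaging comparison carry no visit restriction. This stands in part: a reader might infer that the plan requires two separate p-values, but the text does not force that. It is only the most direct reading. What remains is that no combining analysis is named. The word overall does not supply one, because it contrasts with type of organism and comes with no pooling method.

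**Error inflation.** A reader might infer that the plan doubles the false-positive rate. That needs an either-visit rule, which the documents do not state. Even then the rate in the hypothesised direction is about 4-5%, against 2.5% for a single two-sided test.

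**Unpaired tests.** They have a proper use for hydrogel v silicone hydrogel at one visit, which is a between-person comparison if material order is randomised. Nor are they always conservative: with almost no between-eye correlation they are close to the paired test (type I error 5.7%).

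**Combining is a choice.** The objectives name both materials and EDTA, and Table 4 ties EDTA to material within visits 1-2. An average over two conditions loses power if packaging works in only one: 18/19/23% combined against 31/33/40% for the single-material test, with 42% v 23% in that material and 42% in both arms of the other. This stands, and is why per-material results should be named.

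**Missing pairs.** A reader might infer that nothing governs a person with one pair. The completer rule in section 13.1.3 arguably already excludes someone who misses a visit. The gap is narrower: a completer who lacks one lens result.

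**Preliminary study.** True, and no stated figure is shown to be wrong. But section 13.1.1 says the study is to show whether differences can be detected and to inform the next sample size, which favours one clear estimate from all the pairs.

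**Conclusion.** The point holds as a gap in specification that should be fixed. The plan names per-visit tests permissively, joins no pairs and gives no rule for section 5.2. Single-visit paired tests are valid in themselves; the loss is in precision and in an unambiguous conclusion. At 42% v 23% with the same effect at both visits, power is about 30-40% for one visit against 54-70% combined, and the visits disagree on significance in about 42-48% of trials. At 11% v 4.5% combining still helps, but power is poor either way (about 11% v 21%).

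These sizes rest on assumed rates, assumed correlations and a common effect across materials. The unpaired-test point is the lesser one: conservatism and loss of power grow with between-eye correlation and are small without it.

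**What to change.** In section 13.1.3:

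- **Primary.** Name one packaging analysis: overall contamination (yes/no), visits 1 and 2, two-sided 5%, by a one-sample t-test of each participant's mean paired difference (conventional minus Smart Touch). State that it decides section 5.2. Visit 3 stays outside it.
- **Delete for this comparison** the per-visit qualifier, the group t-test and the rank sum test.
- **One usable pair.** State how such a person enters, consistent with the completer rule and section 13.3. For example, a completer with one lost lens result contributes the one available difference. With 10% of pairs lost at random (assumed), that gives 47/52/64% power at 42% v 23%, against 45/50/60% using only people with both pairs.
- **Secondary.** Packaging within each material (paired), and the packaging-by-material interaction (paired test of each participant's difference between the two packaging differences). Note that material is confounded with EDTA within visits 1-2 and, if material order is not randomised, also with visit.

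The cost is protocol wording only: no added visits, lenses or participants. The downside is that the primary result averages over two material/EDTA combinations, with less power than a single-material test if packaging works in only one.

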13.2. Criteria for Termination of the Trial

The trial will be terminated upon completion of the final study visit by the last participant or unless any of the conditions of Section 7.4 are met. An active participant is one who is enrolled in the study and has not been discontinued.

13.3. Accountability of Data

Individual data points that are missing will be excluded from analysis involving only those specific variables. A participant's complete visit data will not be excluded if some of the observations are missing. Inclusion of outliers in the analysis will be based on the magnitude of change in test statistic with and without the outliers. Outliers will preferably be retained unless there is significant change in test results.

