1. PROTOCOL SYNOPSIS

Table 1

Protocol Title	Microbial contamination rates on the back surface of soft contact lenses in short-term, randomized, contralateral non-dispensing studies.	
Protocol ID Number	SOVS2017-050	
Trial Classification	Evaluation	
Investigator(s)/Site(s)	Eye Research Group @ SOVS The University of New South Wales Sydney, Australia	
Overall Duration of Trial	4 months	
Number of Trial Participants Planned	25 to complete each arm	
Planned Start Date	May 2017	
Primary Objective	To compare the microbial contamination rates on the back surface of hydrogel and silicone hydrogel contact lenses extracted from Smart Touch Technology blister packs versus conventional lens packaging, and the impact of EDTA in the packaging solution after short-term placement on the eye.	
Secondary Objectives	
 ○ To compare the microbial contamination rates of the worn contact lenses to those on the participants' hands/fingers used to conduct lens insertion ○ To determine the sample size required to conduct Phase 2 of the study (a randomized, bilateral cross-over, dispensing study to evaluate ocular redness, comfort and lens contamination rates) based on the detection limits for microbial contamination rates on the back surface of worn contact lenses 	
Primary Safety Variable(s)	Visual acuity Biomicroscopy: ocular redness, corneal details and staining	
Primary Efficacy/Performance Variable	Level of microbial contamination of on the back surface of worn soft contact lenses	
Experimental design	 Retrospective  Prospective  Single group  Multiple group  Parallel group  Cross over  Contralateral	 Single masked (Trial Participant)  Single masked (Investigator)  Double masked  Sponsor masked  Open label  Other
Study product details	Name	Smart Touch Technology
	Manufacturer	Menicon Co. Ltd.
Inclusion criteria	Participants enrolled in the trial must be: 
 ▪ Able to read and comprehend English and give informed consent as demonstrated by signing a record of informed consent; ▪ Be at least 18 years old; 	

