13.1.1. Number of Participants

25 participants will be required to complete the study.

This sample size is an estimate for this preliminary study, to determine whether differences in microbial contamination rates on the back surface of worn soft contact lenses can be detected.

The results of this study will be used to inform the detection limits for microbial contamination rates on the back surface of worn soft contact lenses between the two different types of lens packaging. This will assist to determine the appropriate sample size required to conduct a longer-term dispensing study.

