13.1.2. Significance

A p-value less than or equal to 5% will be considered to be statistically significant.

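### Section 13.3 lets the test result decide whether outliers stay, which can push the false-positive rate for organism counts above 5%; the binary contamination comparison is not affected

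*Combined protocol and SAP*

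**What the plan says.** Section 13.3 (Accountability of Data) gives the criterion first: "Inclusion of outliers in the analysis will be based on the magnitude of change in test statistic with and without the outliers". It then gives a default and its exception: "Outliers will preferably be retained unless there is significant change in test results". The rule is not limited to any type of variable. No other section defines an outlier or says how large a change counts. Section 13.1 mentions range checks and frequency distributions but sets no cutoff.

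Three other places fix what the rule can act on:

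- **Section 13.1.2** sets the threshold: "A p-value less than or equal to 5% will be considered to be statistically significant".
- **Section 13.1.3** makes the overall comparison binary: "Overall contamination rates, expressed as a binary variable, and contamination rates for type of organism will be compared". It also plans means and standard deviations for interval variables and lists tests suited to quantitative data: "Commonly used tests of significance at each visit may include paired t-tests and group t-test for parametric data and Wilcoxon sign rank test".
- **Section 6** says of lenses and finger swabs: "The number and species of organisms will be determined". The synopsis names as the efficacy variable: "Level of microbial contamination of on the back surface of worn soft contact lenses".

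Section 13.1.3 does not name a comparison of counts. The counts are collected, however, and the listed tests make such a comparison plausible.

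**The concern.** An exclusion rule protects the significance level only if it is fixed without reference to the result. Here the rule is the result: the analyst runs the test both ways and keeps or drops values according to how far the answer moves. The preference for retention gives way exactly when the extreme values matter.

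Two things are at stake for count data. The first is the 5% level, because a test on trimmed data referred to its ordinary critical value understates the variability. The second is the content of the data. In a contamination study an extreme count may be a heavily contaminated lens, which is the event of interest. Section 13.1.1 also says the results will inform the detection limits and sample size of the later dispensing study, so losing such values could distort that planning as well.

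**Working it through.** **Inputs from the plan.** Significance at p ≤ 0.05 (section 13.1.2). For the number of pairs, section 13.1.1 says "25 participants will be required to complete the study", and the contralateral design (section 6.1.2) gives one pair of lenses per participant per visit, so n = 25. The 5% is a chosen threshold, so there is no derived figure in the plan to reproduce.

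**Inputs I had to assume.** Two-sided tests, the outlier definition, the trigger and the count distribution. I show a range for the last three.

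**Step 1: what the rule does.** Suppose a significant change means a changed verdict at p = 0.05. Let A be the verdict with all data and B the verdict without outliers.

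- If A = B, the values stay and the report is A, which equals B.
- If A ≠ B, the values go and the report is B.

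The reported verdict is always B. Even-handed use of the rule gives no protection, because the false-positive rate is that of the trimmed test. If the trigger is instead a large enough change in the test statistic, the untrimmed result sometimes stands.

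**Step 2: formulas.** For paired differences d, t = mean(d) / (SD(d)/√n). With n = 25 the critical value on 24 df is 2.064. A difference is flagged if it lies more than k SD from the mean (k = 3 or 2), or more than 1.5 IQR outside the quartiles. After exclusion, t is recomputed with the smaller n and referred to its ordinary t distribution.

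**Step 3: paired t-test under the null, changed-verdict trigger, 40,000 runs.** Simulation error is √(0.05 × 0.95 / 40,000) = 0.11 percentage points.

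| Model for the differences | All kept | 3 SD | 2 SD | 1.5 IQR |
|---|---|---|---|---|
| Normal | 5.0% | 5.3% | 10.1% | 8.6% |
| Lognormal counts, log-SD 1 | 3.9% | 5.4% | 7.3% | 10.6% |
| Half the lenses sterile, log-SD 1.5 | 2.4% | 4.1% | 5.1% | 13.4% |

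Repeat runs agreed to within about 0.5 points. The 13.4% is an extreme case, because the IQR fences there flag 23% of pairs.

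**Step 4: other trigger and other test.**

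- Paired t-test, dropping outliers if |t| changes by 20% or more: 4.5% to 5.8% (3 SD), 5.4% to 10.6% (2 SD), 8.8% to 13.5% (IQR).
- Signed-rank test, changed-verdict trigger, 20,000 runs: 4.8% to 5.3% (3 SD), 5.9% to 8.7% (2 SD), 7.6% to 11.6% (IQR), against 4.5% to 5.0% with all data kept.

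**Step 5: other distributions.** A second set used normal, t with 3 df, lognormal and negative-binomial counts (mean 10, dispersion 0.3, raw and log-transformed). The paired t-test with the changed-verdict trigger gave 4.8% to 5.6% (3 SD), 6.4% to 11.3% (2 SD) and 9.0% to 13.4% (IQR). With all data kept it gave 2.8% to 5.2%.

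**Step 6: low contamination.** With 80% of lenses sterile (log-SD 1.5) the changed-verdict rates are 2.7% / 2.9% / 2.6% (3 SD / 2 SD / IQR), against 1.5% with all data kept. All are below 5%. The IQR fences, however, flag 31% of pairs. With independent lenses only 1 − 0.8² = 36% of pairs contain a contaminated lens, so 0.31/0.36, about 86% of the informative pairs, would be dropped.

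**Step 7: the binary comparison.** A 0/1 value has no extreme magnitude, so a sensible outlier rule removes nothing. An exact McNemar test on 25 pairs, taken here as the natural paired test, has true size 0.7% to 2.5% for contamination rates of 10% to 50%.

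**The case against.** The strongest case on the other side has four parts.

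- **Reach.** The primary endpoint is a contamination rate, the overall comparison is binary, and no count comparison is named. If rates by type of organism are also yes/no per lens, they are untouched too. This stands, and it limits the problem to quantitative analyses that the plan allows but does not specify.
- **Size.** Every cutoff, trigger and distribution is assumed. At 3 SD the inflation is small or absent, and with mostly sterile lenses no rule tested exceeded 5%. This also stands. The excess over 5% depends on how common contamination is as well as on the outlier definition. Even in the sterile case the rate rose relative to keeping all data.
- **Default.** Retention is preferred, and that wording may leave discretion to keep outliers even when the result changes. This helps little, because discretion used after seeing both results is no safer than an automatic rule. The rule does require both analyses to be run, but nothing fixes which is primary or requires both to be reported.
- **Stage.** The study is preliminary. This lowers the severity but does not excuse the rule, since the study still tests at 5% and informs the next one.

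**Conclusion.** The concern holds. As written, section 13.3 makes exclusion of quantitative values depend on the test result, with neither the outlier nor the trigger defined. The effect ranges from negligible with a 3 SD definition to about two to three times the nominal 5% with looser common ones (10.1/5 = 2.0 for normal data at 2 SD; 13.4/5 = 2.7 in the extreme IQR case). There may be no excess over 5% if most lenses are sterile. These sizes rest on assumed distributions, cutoffs and triggers. The defect in the rule does not, and the freedom to choose a cutoff after seeing the data is part of it. The overall binary comparison is unaffected. This should be fixed, but it does not undermine the main comparison.

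**What to change.** Replace the two outlier sentences in section 13.3, for all variables, with wording to this effect:

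> All observed values are kept in the main analysis. A value is excluded only for a documented recording, sampling or laboratory error, decided without knowledge of packaging, material or test result. Any analysis without extreme values is a sensitivity analysis, reported beside the main result and never in its place.

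With all values kept, the simulated false-positive rates were about 5% or lower for both the paired t-test and the signed-rank test. The cost is three sentences of protocol wording. No data, visits or participants are added.
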